## **3 STUDY DESIGN and METHODS of DATA COLLECTION AND DATA ANALYSIS**

### **Design and Implementation of Womb-like Acoustic Environments**

**SHORT TITLE/ACRONYM**

This WP involves comprehensive acoustic research to create a realistic womb-like auditory experience. Exposing infants to their mother's voice and the surrounding sounds involves three steps: recording, sound design and playback. Each step requires special care to accurately reproduce the sound environment the foetus experiences while ensuring safety, privacy, reliability and ease of implementation for the medical staff.

**Recordings.** We will set up tools and equipment to record natural audio from the parents of each child. For the recording phase, the mother will be equipped with a discreet recording system for four days. This system, utilising 32-bit float technology, captures a wide dynamic range without the risk of saturation, allowing for a faithful reproduction of the auditory environment of each family. These initial recordings will provide a diverse array of daily soundscapes that can be randomised to avoid repetition.

Sound processing will involve applying a high-pass filter between 300-400Hz to replicate the in-utero listening experience accurately. Measurements taken with ballistic gel and a hydrophone will ensure precise sound reproduction by capturing the acoustic response of the womb environment. Specific guidelines will be followed for different types of sounds: mother's voice will increase in average by 5.2 dB; voices of other people will be attenuated by 2.1 dB for a man's voice and 3.2 dB for a woman's voice; external environment accentuation of 3.7 dB at 125 Hz and a gradual decrease up to a maximum of 10 dB at 4 kHz. Privacy will be ensured by applying destructive filtering to raw audio and securely storing processed data.

**Secondary recordings:** Following the initial recordings, mothers will be able to send additional audio messages to their child via email or a dedicated WhatsApp number. These recordings will be incorporated into the existing audio dataset and will undergo the same automated processing, filtering, anonymisation, and secure storage procedures as the original recordings. No raw audio from these secondary recordings will be listened to by researchers, and all raw files will be deleted immediately following processing.

**Sound design.** We will simulate in-utero sounds, including maternal heartbeat, respiration and other bodily functions. No suitable recordings of in-utero background sound exist. Therefore,

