**1 BACKGROUND, RATIONALE and THEORETICAL FRAMEWORK**

Premature birth, defined as delivery before 37 weeks of gestation, is a significant global health issue affecting millions of infants each year. While advancements in neonatal care have increased the survival rates of preterm infants, premature infants continue to face unique challenges in their development. Numerous studies have shown that preterm birth increases the risk of cognitive deficits in the preschool and school years. In terms of language, preterm children show poorer auditory discrimination and memory, reading difficulties, poor vocabulary, a specific delay in verbal processing and reasoning, less complex expressive language and lower receptive understanding than their matched controls. Research by the PI has revealed that preterm birth affects, in particular, some aspects of early language development, specifically the acquisition of prosody—the rhythm and melody of speech—while having no significant impact on phonetics—speech sounds—or phonotactics—the rules governing sound combinations—. This indicates a developmental delay in prosodic acquisition for preterm infants, consistent with other studies.

Importantly, hearing becomes functional around 25 weeks of gestation, allowing foetuses to perceive speech in the womb. However, maternal tissues attenuate and filter out higher frequencies above 600–1000Hz, preserving speech melody and rhythm (prosody) while suppressing phonetic details, particularly consonants. As a result, prenatal auditory exposure primarily conveys prosodic information. Rhythmic sounds, like the mother's heartbeat, may act as a pacemaker, shaping early rhythm perception.

Evidence from animal models and simulations suggests that foetuses are exposed to a speech signal rich in prosodic features, further evidence has shown that foetuses can differentiate stimuli using prosodic cues. There is evidence that this prenatal experience shapes infants' perceptual abilities. For instance, newborns are already sensitive to the prosodic grouping and vocalic segments of their native language. Furthermore, studies using EEG responses in newborns demonstrated that prenatal exposure to specific changes in vowels and pitch led to

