**SHORT TITLE/ACRONYM**

we will use film sound effects and sound design techniques, carefully respecting previous frequency and sound level measurements, as well as the timing of these events. This creates a realistic background sound environment for the infant. The final design will be mixed with the edited parent recordings.

**Playback.** During their NCU stay, infants transition from incubators to cots, and playback will be used in both. Both systems will prioritize safety, adaptability to medical needs, high-quality audio, and easy maintenance. Developed in close collaboration with NCU staff, they will ensure feasibility and acceptability.

It is crucial to emphasize that in addition to adhering to safety standards for the infant, we will pay special attention to sound levels and meet the standards previously suggested. These levels will be meticulously studied, measured, and regularly checked using reference microphones to ensure they are safe and appropriate; emergency shut-off switches will be included for both systems.

After measuring the incubators' sound profile (resonance, frequency nodes, etc.), we will attach an external conduction speaker to the lid for spatial sound diffusion, avoiding intrusive equipment inside. For cots, externally positioned speakers behind the baby's head and acoustic panels will minimize sound leakage. The setup will be mounted on a mobile cart for easy handling. While complete sound isolation is impossible, the proximity of the sound source ensures it remains the dominant auditory input, creating a form of psychoacoustic isolation.

Our advisory group—including NCU staff (consultant neonatologists, nurses, occupational therapists, and psychologists), four parents of preterm children, and charity partners SSNAP and Speech and Language UK—has been involved since the project's inception. Their feedback has shaped the proposed approach and will continue to guide refinements before implementation.

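### The protocol specifies a high-pass filter for the parental recordings, the reverse of the womb acoustics it sets out to reproduce; low-pass is very probably meant

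*Protocol*

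**What the plan says.** Protocol section 3, under Design and Implementation of Womb-like Acoustic Environments (Recordings), states: "Sound processing will involve applying a high-pass filter between 300-400Hz". The rest of that sentence gives the aim as a faithful imitation of what the foetus hears. The same paragraph sets level rules by type of sound, including "external environment accentuation of 3.7 dB at 125 Hz and a gradual decrease up to a maximum of 10 dB at 4 kHz". It adds: "Measurements taken with ballistic gel and a hydrophone will ensure precise sound reproduction". Under Secondary recordings, later audio messages from mothers "will undergo the same automated processing, filtering, anonymisation, and secure storage procedures as the original recordings".

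Section 1 (Background) gives the acoustic rationale. There, "maternal tissues attenuate and filter out higher frequencies above" 600–1000 Hz, "preserving speech melody and rhythm (prosody) while suppressing phonetic details, particularly consonants". Section 1 concludes that "prenatal auditory exposure primarily conveys prosodic information".

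The Predictions paragraph in section 3 rests on this mechanism. If delay comes from missing prenatal exposure to prosody, it should appear in the standard-care preterm group and not in the womb-simulated group.

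**The concern.** The filter sentence and the rationale point in opposite directions. The word sits in the methods text that defines what the intervention group hears, not in background prose.

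Followed literally, the processing would weaken parental speech in the lower part of the band that section 1 says is preserved. It would keep the higher-frequency phonetic detail that section 1 says is suppressed. The womb-simulated group would then not receive the exposure on which the prediction depends, and a null result could not be read as evidence against the hypothesis.

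The mistake might also be impossible to undo. Section 6 (Confidentiality and Data Protection) has raw audio deleted once processing is complete. For secondary recordings, section 3 has deletion follow processing immediately, and researchers do not listen to the raw files.

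**Working it through.** The protocol gives no filter response to reproduce, so the check has two parts.

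**1. Direction, from the text alone**

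| Place in the protocol | Low frequencies | High frequencies |
|---|---|---|
| Section 1, womb acoustics | kept | lost above 600–1000 Hz |
| Section 3, external-sound rule | raised 3.7 dB at 125 Hz | falling, by up to 10 dB at 4 kHz |
| Section 3, filter as written (high-pass, 300–400 Hz) | lost | kept |

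The first two rows have a low-pass shape and the third has the reverse. The term low-pass appears nowhere in the protocol, and no other place qualifies the filter type.

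**2. Size, for illustration**

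Inputs from the protocol: cut-off fc = 300 or 400 Hz, and the frequencies it names (125, 300, 400, 600, 1000 and 4000 Hz). Assumption: a Butterworth filter of order n = 1, 2 or 4, since neither family nor order is stated.

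- High-pass loss in dB = 10·log10(1 + (fc/f)^(2n))
- Low-pass loss in dB = 10·log10(1 + (f/fc)^(2n))

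Worked example, high-pass, fc = 300, f = 125, n = 1: (300/125)² = 5.76, and 10·log10(6.76) = 8.3 dB.

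High-pass loss (dB), for n = 1 / 2 / 4:

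| f (Hz) | fc = 300 | fc = 400 |
|---|---|---|
| 125 | 8.3 / 15.3 / 30.4 | 10.5 / 20.2 / 40.4 |
| 300 | 3.0 / 3.0 / 3.0 | 4.4 / 6.2 / 10.4 |
| 400 | 1.9 / 1.2 / 0.4 | 3.0 / 3.0 / 3.0 |
| 600 | 0.97 / 0.26 / 0.02 | 1.60 / 0.78 / 0.17 |
| 1000 | 0.37 / 0.04 / 0.00 | 0.64 / 0.11 / 0.00 |
| 4000 | 0.02 / 0.00 / 0.00 | 0.04 / 0.00 / 0.00 |

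Low-pass loss (dB) at the same cut-offs, for n = 1 / 2 / 4:

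| f (Hz) | fc = 300 | fc = 400 |
|---|---|---|
| 125 | 0.70 / 0.13 / 0.00 | 0.40 / 0.04 / 0.00 |
| 1000 | 10.8 / 21.0 / 41.8 | 8.6 / 16.0 / 31.8 |
| 4000 | 22.5 / 45.0 / 90.0 | 20.0 / 40.0 / 80.0 |

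The order changes the size of the loss but never its direction. As written, the loss is partial: from 400 Hz up to 600–1000 Hz the signal passes with at most 3.0 dB lost.

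The low-pass rows also show that the word alone does not settle the signal. A 300–400 Hz cut-off is lower than the 600–1000 Hz of section 1. It would take at least 20 dB off at 4 kHz, whereas the external-sound rule allows a decrease of no more than 10 dB there. The protocol does not say how the filter and the level rules combine.

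**The case against.** The strongest reply is that this is one wrong word whose intended meaning is plain. The sentence's own aim, section 1, the external-sound rule and the prosody mechanism all settle the direction. Harm would require the team to implement the word literally and then miss it in the gel and hydrophone measurements, in the advisory group's feedback, which "will continue to guide refinements before implementation", and in the testing of incubators without infants. Simulated heartbeat and body sounds are mixed in separately. Allocation, outcomes, the analysis model and sound-level safety are untouched. The decibel ranges reflect an assumed filter, and 300–400 Hz has not been shown to be wrong.

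Most of this stands. The error is probably a slip, the planned checks may well catch it, and the ranges are only illustrative. The cut-off needs confirming and is not shown to be an error. In the secondary-recordings sentence, filtering could refer partly to privacy filtering, so the reach of the word there is likely but not certain.

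What does not follow is that the text can stay. None of the planned steps corrects the protocol. If the team applies a low-pass filter, it departs from its written method, and section 7.5 requires deviations to be documented and reported. If it follows the text, the signal is wrong and the raw recordings may be gone.

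**Conclusion.** The concern holds and should be fixed. The filter named in section 3 is opposite in direction to the womb acoustics in section 1 and to the external-sound rule in its own paragraph. That conclusion rests on the text alone.

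The size depends on the assumed Butterworth filter of order 1 to 4. As written, the loss is about 8–40 dB at 125 Hz and at most about 0.6 dB at 1000 Hz. With low-pass at the same cut-off, it is at most 0.7 dB at 125 Hz and about 9–42 dB at 1000 Hz. That low-pass was intended is a well-supported inference. The consequence concerns the fidelity of the intervention and the reading of a null result, and only if the text is followed literally.

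**What to change.** In section 3 (Recordings), replace high-pass with low-pass. In the same sentence, confirm the cut-off, either 300–400 Hz as written or the 600–1000 Hz of section 1. Do this before any family audio is processed and its raw file deleted.

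Two optional additions would help:

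- State how the filter combines with the decibel rules for each type of sound.
- Check the filtered output against the planned gel and hydrophone response, using the research team's own infant-directed speech recording so that no family audio is at risk.

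The cost is one word and a confirmed number. No new equipment or procedure is needed.

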**SHORT TITLE/ACRONYM**

we will use film sound effects and sound design techniques, carefully respecting previous frequency and sound level measurements, as well as the timing of these events. This creates a realistic background sound environment for the infant. The final design will be mixed with the edited parent recordings.

**Playback.** During their NCU stay, infants transition from incubators to cots, and playback will be used in both. Both systems will prioritize safety, adaptability to medical needs, high-quality audio, and easy maintenance. Developed in close collaboration with NCU staff, they will ensure feasibility and acceptability.

It is crucial to emphasize that in addition to adhering to safety standards for the infant, we will pay special attention to sound levels and meet the standards previously suggested. These levels will be meticulously studied, measured, and regularly checked using reference microphones to ensure they are safe and appropriate; emergency shut-off switches will be included for both systems.

After measuring the incubators' sound profile (resonance, frequency nodes, etc.), we will attach an external conduction speaker to the lid for spatial sound diffusion, avoiding intrusive equipment inside. For cots, externally positioned speakers behind the baby's head and acoustic panels will minimize sound leakage. The setup will be mounted on a mobile cart for easy handling. While complete sound isolation is impossible, the proximity of the sound source ensures it remains the dominant auditory input, creating a form of psychoacoustic isolation.

Our advisory group—including NCU staff (consultant neonatologists, nurses, occupational therapists, and psychologists), four parents of preterm children, and charity partners SSNAP and Speech and Language UK—has been involved since the project's inception. Their feedback has shaped the proposed approach and will continue to guide refinements before implementation.

## **Implementing Womb-like Environments in NCUs**

**SHORT TITLE/ACRONYM**

Final outputs will be implemented and tested in incubators, initially without infants (as part of WP1). Once extensively tested, the system will be introduced to incubators with infants having parental consent.

Participants. A total of 150 infants will be tested, accounting for a 20% attrition rate due to multiple experiments (10%) and longitudinal design (10%). This ensures sufficient participants per group (WS-PTg, SC-PTg, CO-FTg) for statistical analyses ( $\alpha=0.05$ , power=0.80, GPower 3.1). The estimate is based on effect sizes ( $d=0.59-0.80$ ) from prior studies on early speech perception and language outcomes in preterm infants. Participants will include:

- 1) Womb-simulated PT group (WS-PTg): Forty healthy preterm infants meeting five primary criteria:
  1. Gestational age  $\geq 26$  and  $\leq 34$  weeks.
  2. Absence of major cerebral damage (e.g., periventricular leukomalacia, intraventricular haemorrhage...).
  3. No indication of visual or hearing impairment.
  4. No family risks of developmental or language disorders.
  5. From monolingual English-speaking families.

Infants eligible to participate in the WS-PTg will be identified by the NCU team as soon as possible after their arrival to the unit and parents of these infants will be approached by one of the neonatal nurses to ask if they would want to take part in the project. Families who have given consent will be approached by the research team and given the necessary equipment to do the audio recordings. Meanwhile, a general recording of infant-directed speech recorded by the research team will be used until parental recordings are available. Infants will be exposed to the recordings until they are discharged from the NCU or they reach their due date.

- 2) Standard care PT group (SC-PTg): Forty healthy preterm infants who meet the same criteria outlined above will be recruited using the same strategy. Infants assigned to the SC-PTg will, when possible, be those who have already been discharged from the NCU.
- 3) Comparison FT group (CO-FTg): Forty healthy full-term infants born at  $\geq 37$  weeks who also meet criteria 2–5 outlined above.

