**Full-term infants and potential standard-care preterm participants recruited outside NCUs**

Full-term infants, and potentially some preterm infants in the standard-care group, will be identified through the Oxford Brookes BabyLab participant database. This database consists of families who have proactively registered their interest in taking part in developmental research and have provided consent to be contacted about future studies.

Recruitment to the BabyLab database occurs via general publicity, including leaflets, posters, and the BabyLab website. These materials advertise participation in BabyLab research broadly rather than a specific study. Eligible families are contacted by email when their child reaches the appropriate age and are then provided with full written and verbal information about the study before any consent is sought.

The researcher will also spend some time in the ultrasound unit where women/partners are waiting for their scans and talk about the study. At this point, parents will receive a flyer and interested parents will be asked to complete an expression of interest card to join the BabyLab Participant Database.

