**SHORT TITLE/ACRONYM**

## **7.6 Data protection and patient confidentiality**

All investigators and study site staff will comply with the requirements of the Data Protection Act 1998 regarding the collection, storage, processing, and disclosure of personal information and will uphold the Act's core principles.

Collection and coding of data: Personal information from participants will be collected via consent forms and demographic questionnaires. Each participant will be assigned a unique identifier, and identifiable information will be stored separately from research data. Audio and video recordings of infants during tasks will be pseudo-anonymised using the same identifier.

Secure storage: Identifiable information will be stored in a locked cabinet within a restricted-access area of the Babylab. Electronic files will be stored on encrypted, password-protected folders on University computers. Linking codes between identifiers and personal data will be kept separately from research data to maintain confidentiality.

Access control: Access to personal data will be limited to the research team directly involved in participant management and data analysis. No medical data will be accessed by the research team; only data provided directly by participants through questionnaires or recordings will be used.

Data transmission: When data are shared with co-investigators or for analysis, only pseudo-anonymised datasets will be transmitted via secure, encrypted channels.

Data retention: Identifiable data will be retained for over three years for participants who consent to be contacted for future studies, in line with Brookes BabyLab policy. Consent forms and demographic sheets will be stored securely for 10 years in accordance with University regulations. Fully anonymised datasets will be archived and made publicly available at the end of the project.

Data custodian: The Principal Investigator will act as the data custodian, ensuring compliance with data protection regulations, overseeing secure storage, and managing access to the datasets.

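### The two preterm groups are recruited at different times and by different routes, with no allocation rule, no matching between them and no adjustment in the primary models, so the main contrast is confounded to an unknown degree and in an unknown direction

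*Protocol*

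**What the plan says.** All of the following is in the protocol.

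- **Exposed group, entry.** Section 3 (Participants) says that eligible WS-PTg infants "will be identified by the NCU team as soon as possible after their arrival to the unit". Section 5.3.1 has the clinical team screen records, make the first approach and refer interested families to the research team.
- **Standard-care group, entry.** Section 3 says these infants meet the same criteria and "will be recruited using the same strategy". The next sentence reads: "Infants assigned to the SC-PTg will, when possible, be those who have already been discharged from the NCU".
- **Standard-care group, approach.** Under section 5.3.1 the clinical team identifies and approaches families, who return an expression-of-interest card to a box that the research team empties.
- **Second source.** Section 5.3.1 adds that "potentially some preterm infants in the standard-care group, will be identified through the Oxford Brookes BabyLab participant database". Sections 4 and 5.3 say the same, also with the word potentially. These families registered themselves and are contacted once the child is of suitable age; that age is not defined.
- **Control of confounding.** Sampling is purposive (section 5.2.2). Matching is described only for full-term infants (sections 3 and 5.2.2). Section 3 (Analyses) keeps SES, gestational age and birth weight out of the primary models and explores them in secondary analyses.
- **Clinical data.** Section 7.6: "No medical data will be accessed by the research team".
- **Use of the contrast.** Section 3 (Predictions) expects a delay in the standard-care group and none in the exposed group if missing prenatal prosody is the cause.

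**The concern.** Whether the sound environment works is answered by comparing the two preterm groups. A causal reading requires that they would have had similar outcomes without it. Here the time of entry, the approach and possibly the source all differ by group, and no stage of the design or the primary analysis corrects for this.

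Shared criteria do not settle the matter, because the same criteria applied at different times can select different infants. Brain injury or hearing loss may be unknown near admission and known by discharge. A recruitment imbalance of this kind is cheap to prevent before enrolment and only partly repairable by analysis afterwards.

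**Working it through.** **1. The planned sample size.** Three groups of 40 with 20% attrition give 3 × 40 / (1 − 0.20) = 150, the stated total. For a pairwise two-sided t-test at α = 0.05 with 40 per group (the protocol does not state sidedness), power is 0.74 at d = 0.59 and 0.94 at d = 0.80, the ends of the planning range. It reaches 0.80 at d = 0.634, inside that range. The point below is therefore about selection, not sample size.

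**2. The two preterm routes side by side.**

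| | Exposed (WS-PTg) | Standard care (SC-PTg) |
|---|---|---|
| Preferred entry | soon after admission | after discharge, when possible |
| Screening in the unit | clinical team | clinical team |
| Approach in the unit | direct referral to research team | opt-in card |
| Second source | none | database, potentially for some |
| Clinical check for database infants | not applicable | none described; the research team sees no medical data |
| Matching to the other preterm group | none | none |

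One row agrees. Timing, approach and possible source do not, so the statement about a common strategy conflicts with section 5.3.1. Section 5.2.2, which has preterm infants identified through the NCU, also conflicts with the database route.

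**3. Direction.** The text supports arguments both ways.
- Standard-care infants are screened later, when more exclusions may be known. This would tend to make that group healthier.
- Section 5.1.1 also excludes medical instability. An infant unstable early may have recovered by discharge and be eligible for standard care, while an exposed candidate in the same state is excluded near admission. This would tend to make the exposed group healthier.
- Database families are self-registered volunteers. Exposed families volunteer too: the mother wears a recorder for four days (section 3, Recordings).

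**4. Missing outcomes.** An infant lost before the 7.5-month visit has no looking-time data and adds nothing to the mixed model. If families enter at different ages, the time at risk of such loss differs by group, and the model does not correct for it.

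**5. What an offset would do (illustration).** Let *b* be an assumed difference in SD units between the preterm groups on the per-infant score being compared, with no true effect. The two-sided t-test then follows a non-central t distribution with 2*n* − 2 degrees of freedom and non-centrality *b*·√(*n*/2). With *n* = 40, √20 = 4.47; with *n* = 50, √25 = 5.

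| Assumed *b* | Non-centrality, *n* = 40 | Rejection, *n* = 40 | Rejection, *n* = 50 |
|---|---|---|---|
| 0.1 | 0.45 | 7% | 8% |
| 0.2 | 0.89 | 14% | 17% |
| 0.3 | 1.34 | 26% | 32% |

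The nominal rate is 5%. For a fixed offset the false-positive rate rises with *n*, so recruiting more infants does not help. An offset against the intervention would mask a real effect instead.

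**The case against.** The case on the other side has real substance.

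- **The routes overlap.** In the unit, the same clinical team screens both preterm groups against the same criteria. This stands: the claim of a common strategy is partly true. What differs is the preferred timing, the card step and the possible second source.
- **The database is only a possibility.** This also stands. Concerns about unverified eligibility and late contact apply only to whatever subset comes that way. A family that returns a card during the NCU stay waits about as long as an exposed family.
- **Confounders are examined.** SES, gestational age and birth weight appear in secondary analyses. That helps, but they do not capture clinical course, the time at which criteria were judged, or family motivation, and the primary contrast stays unadjusted.
- **Discharged controls may limit contamination.** Section 3 (Playback) concedes that full sound isolation is impossible. The protocol does not give this as its reason, and the aim would not require a different eligibility time or source.
- **Random allocation is a different design.** Section 5.2.2 argues against random sampling, not against random allocation. Randomising would be stronger, but the point does not depend on it.

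A reader might go further and infer that standard-care infants are selected to be healthy, retained and research-minded while exposed infants are not, so that the bias runs against the intervention by a calculable amount. The documents do not support this. Both groups are described as healthy, the section 5.1.1 exclusions cover all preterm infants, and exposed families also self-select. Nor do the documents show that standard-care infants will be born in an earlier period; no recruitment calendar is given.

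**Conclusion.** The point holds as uncontrolled confounding of the exposed versus standard-care preterm contrast, of unknown size and direction, together with a misstatement about the recruitment strategy. It rests on the protocol's own text: different preferred entry times, different approach routes, a possible second source, no allocation rule, no matching between the preterm groups, and no adjustment for SES, gestational age or birth weight in the primary models.

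The rejection rates of about 7%, 14% and 26% rest on assumed offsets of 0.1, 0.2 and 0.3 SD, a two-sided t-test on one score per infant, 40 infants per group and no true effect. They show sensitivity and do not estimate the bias in this trial. The mixed model will give somewhat different rates. The matching of full-term infants, which section 3 says strengthens causal inference, does nothing for this contrast.

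**What to change.** 1. **Common eligibility time.** Apply the section 5.1.1 exclusions to both preterm groups at one later point, such as discharge or due date, from the clinical team's record. State the medical-instability criterion over the same part of the stay in both groups. Judging standard-care infants on the record as it stood near admission would not do, since it would admit infants with known injury whom section 5.1.1 excludes. For exposed infants this check falls after exposure, so report the number and reasons excluded in each group.
2. **Source, matching and adjustment.** Draw standard-care infants preferentially from the same NCU's admissions. Frequency-match them to the exposed group on gestational-age band, sex and SES, extending what is already planned for full-term infants on gender and SES. Include gestational age and SES in the model for this contrast.
3. **Database infants.** Accept them only when the clinical team, with parental consent, confirms the criteria. Repeat the contrast without them.
4. **Wording.** Replace the statement about a common strategy with the actual routes, align section 5.2.2 with section 5.3.1, and soften the causal wording in section 3.

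The cost is a protocol amendment, consent wording for a record check, and slightly slower standard-care recruitment. If the clinical team returns only whether the criteria are met, section 7.6 can stand. Gestational age would then have to come from parents, or section 7.6 be amended to let the clinical team supply it. Some database infants may be lost if their records cannot be checked.
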